Procedure	Screening V1 (up to 30 days before Day 1)	V2 Day -9	Treatment Period (13 weeks)							Follow- up ² V9 (42 days post last dose)	Notes
			V3 Baseline Day 1	V4 Day 14	V5 Day 28	V6 Day 56	V7 Day 80	V8 Last dose 90	Unscheduled visit ¹		
Sniff Nasal Inspiratory Pressure	X		X			X		X			
Leg strength	X		X		X	X		X		X	
Handgrip strength	X		X					X			
Short Physical Performance Battery	X		X		X	X		X		X	
Incremental Shuttle Walk Test		X	X					X			Practice incremental shuttle walk test conducted at day -9
Endurance Shuttle Walk Test			X					X			
COPD Assessment Test			X			X		X			
St George Respiratory Questionnaire COPD (SGRQ-c)			X					X			
Patient Global Rating of Severity			X					X			
Patient Global Impression of Change				X	X	X		X		X	
Daily PROactive Physical Activity in COPD instrument and Physical Activity Monitor	X	X ⁷				X	X ⁷				Physical activity monitor dispensed at screening, day -9, day 56 and day 80 visits. Activity monitor should be worn for 7 days at each timepoint and returned at the next visit.
Monitored home exercise program		X	X	<=====>				X			Participants will receive training for the exercise program at Day -9, and will formally begin exercises on day 1
Patient exit interview										X	
Randomization			X								All Baseline assessments must be obtained prior to randomization.
Study treatment provided to participant			X		X	X					The subject should take their first dose of study treatment in the clinic after randomization.

Procedure	Screening V1 (up to 30 days before Day 1)	V2 Day -9	Treatment Period (13 weeks)							Follow- up ² V9 (42 days post last dose)	Notes
			V3 Baseline Day 1	V4 Day 14	V5 Day 28	V6 Day 56	V7 Day 80	V8 Last dose 90	Unscheduled visit ¹		
Study treatment			X	←=====→				X			Participants should dose study treatment in the clinic at each clinic visit during the treatment period.
Study treatment accountability by study site			X	X	X	X		X			The required counting of pills by site staff to check compliance is not considered redispensing the study medication.
AE review			X	←=====→					X		
SAE review			X	←=====→					X		
Concomitant medication review			X	←=====→					X		
Optional sub-study measures											
Cardiac and liver MRI (additionally prostate MRI in males)			X ⁸					X ⁸			MRI is an optional assessment undertaken at participating centres only.

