The selection of individual medications and dosages for the treatment of COPD is left to the discretion of the investigator, although it is recommended that treatment regimens conform to current, local, national standard of care, and that treatment is optimized prior to screening with no further changes to treatment anticipated between the randomization visit and the end of the study.

Eligible participants will be randomized as described above following completion of the Baseline assessments. Participants will be sent home with a 42-day supply of study medication. Participants will be asked to return to the clinical unit on approximately days 14, 28, 56, 80 and 90 as specified in the SoA (Section 2) Participants will be resupplied with study treatment at the Day 28 and 56 visits.

All visits should be conducted in a single day within the study visit window (Section 2). Participants will be provided a meal between completion of fasting labs and start of other study assessments.

All participants will be asked to participate in a home exercise program reflecting usual care (e.g. a pulmonary rehabilitation program). The home exercise program will consist of daily walking, along with several resistance or weight-bearing exercises, such as bicep curls, upright rows, step ups, and a sit-to-stand manoeuvre, as allowed by site staff at screening. Site staff will supervise performance of the initial exercises to assess which of the four exercises can be prescribed to participants, as well as setting the baseline intensity for the exercises and clarifying instructions from the home exercise Application. Home exercises will be monitored with the use of a consumer-based activity monitor during the activities outside the clinic [Mitchell, 2014]. Guidance for performing exercises and setting goals will be given by the home exercise Application from the baseline visit onwards, however participants will have the opportunity to raise any concerns they have with site staff. See Study Reference Manual (SRM) for additional detail.

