7.1. Treatments Administered

Study Treatment Name:	GSK2881078	Placebo
Dosage formulation:	Capsule	Capsule
Unit dose strength(s):	0.5mg, 1.0mg	N/A

Dosage level(s)	1.0mg for women (2 x 0.5mg capsules) once daily 2.0mg for men (2x 1.0mg capsules) once daily	2 capsules once daily
Route of Administration	For oral use only	For oral use only
Dosing instructions:	Take as directed	Take as directed
Packaging and Labeling	Capsules will be provided in a bottle. Each bottle will be labeled as required per country requirement.	Capsules will be provided in a bottle. Each bottle will be labeled as required per country requirement.

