7.6. Treatment Compliance

- When participants are dosed at the site, they will receive study treatment directly from the investigator or designee, under medical supervision. The date and time of each dose administered in the clinic will be recorded in the source documents. The dose of study treatment and study participant identification will be confirmed at the time of dosing by a member of the study site staff other than the person administering the study treatment.
- When participants self-administer study treatment(s) at home, compliance with GSK2881078 will be assessed through querying the participant during the site visits and documented in the source documents and CRF. A record of the number of GSK2881078 tablets dispensed to and taken by each participant must be maintained and reconciled with study treatment and compliance records. Treatment start and stop dates, including dates for treatment delays and/or dose reductions will also be recorded in the CRF.
- Compliance at each visit will be determined as follows:
$$(\# \text{ dispensed} - \# \text{ returned}) \times 100 / (\# \text{ days since last visit})$$
- Participants estimated to have taken less than 80% or more than 120% of study treatment capsules at two consecutive visits will be considered noncompliant. All attempts should be made to improve the participant's compliance in taking study treatment if the participant is continuing in the study.

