## 12.6. Appendix 6: Derived and Transformed Data

### 12.6.1. General

Multiple Measurements at One Analysis Time Point

 
• Mean of the measurements (not in case of visit slotting) will be calculated and used in any derivation of summary statistics but if listed, all data will be presented.
 
• If there are two values within a time window (as per Section 12.3.1) the value closest to the target day for that window will be used. If values are the same distance from the target, then the mean will be taken.
 
• Participants having both High and Low values for Normal Ranges at any post-baseline visit for safety parameters will be counted in both the High and Low categories of “Any visit post-baseline” row of related summary tables. This will also be applicable to relevant Potential Clinical Importance summary tables.
 

Study Day

 
• Calculated as the number of days from First Dose Date: 
 
• Ref Date = Missing → Study Day = Missing
 
• Ref Date < First Dose Date → Study Day = Ref Date – First Dose Date
 
• Ref Date ≥ First Dose Date → Study Day = Ref Date – (First Dose Date) + 1
 
 
 
 
Note that Treatment Start Date is considered as Study Day 1.

Post-baseline

 
• Post-baseline refers to the combined time periods of On-treatment and Post-treatment.
 

Change from Baseline
= Post-baseline - Baseline
Ratio to Baseline
= $\exp(\log(\text{Post-baseline}) - \log(\text{Baseline}))$
Percent Change from Baseline
= $100 * (\text{Post-baseline} - \text{Baseline}) / \text{Baseline}$
Treatment compliance

= <math>100 * (\text{Total Amount Taken} / (\text{Treatment duration in days} * 2))</math>
 
Total Amount Taken = Total tablets dispensed – Total tablets returned – Total tablets lost.

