### 12.6.3. Safety

Extent of Exposure	

 
Number of days of exposure to study drug will be calculated based on the formula: Duration of Exposure in Days = Treatment Stop Date – (Treatment Start Date) + 1 The number of days exposure therefore does not take into account dose interruptions.
 
Participants who were randomized but did not report a treatment start date will be categorised as having zero days of exposure.
 
Actual amount taken (number of tablets) = Total tablets dispensed – Total tablets returned – Total tablets lost.
 
Females will take 1 mg everyday (2*0.5mg tables) and males will take 2 mg (2*1mg). So, the actual dose (mg) taken will be the same as actual amount taken for males and for females it will be actual amount taken divided by 2.
 
The cumulative actual dose (mg) will be the sum of the actual doses taken.
 
	
Adverse Events	
Onset Time Since 1st Dose (Days)	If Treatment Start Datetime $\leq$ AE Onset Datetime , then AE Onset Datetime - Treatment Start Datetime +1 If time part is missing in any of the Datetime, then use the Treatment Start date and AE

Extent of Exposure	
	Onset date in calculation and missing otherwise.
Duration (Days)	AE Resolution Datetime – AE Onset Datetime + 1 If time part is missing in any of the Datetime, then use the AE Resolution date and AE Onset date in calculation and missing otherwise.
Drug-related	If the question 'is there a reasonable possibility that AE may have been caused by the Study Treatment' is marked 'YES' on CRF or is missing.

MRI

 
Body Surface Area (BSA) (m^2) = 0.007184 * Weight (kg)0.425 * Height (cm)0.725
 
Left Ventricular End Systolic Volume Index (LVESVi) = <math>\frac{LVESV}{\text{Body Surface Area}}</math>
 
Left Ventricular End Diastolic Volume Index (LVEDVi) = <math>\frac{LVEDV}{\text{Body Surface Area}}</math>
 

Adverse Events
Adverse Events of Special Interest (AESI))
The following table presents the AESI. AESI which are not SMQs are made up of a selection of preferred terms (PTs) defined by GSK. The complete list of AESI, including the PTs which contribute to each of the AESI will be provided by Safety and Medical Governance using the MedDRA version current at the time of reporting.

AESI	Group of terms (MedDRA SMQ, HLT or individual PTs)																		

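### The protocol's compliance formula leaves out the two-capsule daily dose and need not cover the counted interval, so full adherence computes as 200% or more and is labelled noncompliant

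*Protocol*

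**What the plan says.** Protocol 7.6 introduces its formula with "Compliance at each visit will be determined as follows". It subtracts capsules returned from capsules dispensed, multiplies by 100 and divides by the days since the last visit. The rule applied to the result is: "Participants estimated to have taken less than 80% or more than 120% of study treatment capsules at two consecutive visits will be considered noncompliant".

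The dose is two capsules once daily in every arm. Protocol 7.1 gives men "2.0mg for men (2x 1.0mg capsules) once daily", women two 0.5 mg capsules and placebo participants two capsules. SAP 12.6.3 agrees: "Females will take 1 mg everyday (2*0.5mg tables) and males will take 2 mg (2*1mg".

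On supply, protocol 5.1 says "Participants will be sent home with a 42-day supply of study medication" and "Participants will be resupplied with study treatment at the Day 28 and 56 visits". The schedule of activities (protocol section 2) marks accountability on Days 1, 14, 28, 56 and 90, but not at the Day 80 visit. It adds: "The required counting of pills by site staff to check compliance is not considered redispensing the study medication".

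SAP 12.6.1 defines treatment compliance over the whole treatment period, with "Treatment duration in days" multiplied by 2 as the denominator. The footnote to listing shell POP_L9 (SAP Appendix 12) multiplies by an undefined *frequency* instead. The table of changes to the protocol's analysis plan (SAP 2.1, Table 1) does not mention that the SAP and protocol formulas differ.

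**The concern.** The numerator of the protocol formula is in capsules and the denominator is in days, so the result is a percentage only if one capsule is due per day. Two are due. The 80–120% limits presuppose that full adherence reads about 100%, and here it does not.

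The numerator and denominator also need not refer to the same period. No drug is dispensed at Day 14, so at Day 28 the dispensed count may reach back to Day 1 while the days run from Day 14. At Day 90 the capsules cover the time since Day 56, but the last visit was Day 80.

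At stake is the site-level noncompliance label. Protocol 7.6 asks for efforts to improve compliance in labelled participants who continue, and protocol 8.2 lets the investigator withdraw a participant for compliance reasons. As printed, the rule points these actions at adherent participants, passes those taking half their capsules, and cannot tell full adherence from overuse.

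**Working it through.** **Inputs.** Two capsules a day (protocol 7.1). Visits on Days 1, 14, 28, 56, 80 and 90; dispensing on Days 1, 28 and 56; counts on Days 1, 14, 28, 56 and 90 (protocol sections 2 and 5.1). First supply 42 days × 2 = 84 capsules. Assumptions: nominal visit days, count taken before that day's clinic dose, clinic doses drawn from the participant's supply, no losses.

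**The plan's own scale.** The 80–120% band implies that full adherence is 100%. SAP 12.6.1 reproduces this: 180 capsules / (90 days × 2) = 100%. The protocol formula does not.

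**Count and days over the same interval, full adherence.**

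| Count | Days since previous count | Capsules used | Protocol 7.6 | Capsules / (2 × days) |
|---|---|---|---|---|
| Day 14 | 13 | 26 | 26/13 = 200% | 26/26 = 100% |
| Day 28 | 14 | 28 | 28/14 = 200% | 28/28 = 100% |
| Day 56 | 28 | 56 | 56/28 = 200% | 56/56 = 100% |
| Day 90 | 34 | 68 | 68/34 = 200% | 68/68 = 100% |

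Days 14 and 28 are two consecutive results above 120%, so the label applies by Day 28.

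**What the band admits.** On matched intervals the computed value is 200 × true adherence. Computed values of 80%, 100% and 120% therefore correspond to 0.8, 1.0 and 1.2 capsules a day, or true adherence of 40%, 50% and 60%.

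**Literal intervals (capsules since last dispensing, days since last visit).**

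- Day 28, if the Day 14 count is not carried forward as an opening balance: 84 − 30 = 54 capsules since Day 1. Computed: 54/14 = 386%. With only the factor of 2 added: 54/(2 × 14) = 193%.
- Day 90: 68 capsules since Day 56, and 10 days since Day 80. Computed: 68/10 = 680%. With only the factor of 2 added: 68/(2 × 10) = 340%.

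On this reading the factor of 2 alone is not enough; the interval must be defined too.

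**Sensitivity.**

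- If visit-day clinic doses came from separate stock, full adherence computes as 24/13 = 184.6%, 26/14 = 185.7%, 54/28 = 192.9% and 64/34 = 188.2%.
- If the visit-day doses at both ends of the interval are charged to it, the values are 28/13 = 215.4%, 30/14 = 214.3%, 58/28 = 207.1% and 70/34 = 205.9%.
- Counting in two-capsule doses on matched intervals gives 100%, but protocol 7.6 speaks of tablets dispensed and of a percentage of capsules.

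Every reading in capsules exceeds 120% at every count.

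**POP_L9.** If *frequency* is read as once daily, 180/(90 × 1) = 200%, against 100% from SAP 12.6.1.

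**The case against.** The missing factor is hard to dispute; the case against concerns the rest.

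- **The interval point is an ambiguity.** The last visit, in a capsule-count formula, can be read as the last counted visit, which gives exactly 200%; 386% and 680% need a mixed reading. This stands in part. The Day 28 figure depends on whether the Day 14 balance is carried forward. The Day 90 figure follows from the literal text, because Day 80 is a scheduled visit with no count.
- **200% is not a strict floor.** Clinic doses from separate stock would give 185–193%. The documents do not say such stock exists, and treatment is provided only on Days 1, 28 and 56. The label would be the same.
- **The practical effect is small.** Sites also question participants and reconcile counts, the only stated consequence is encouragement, and withdrawal under 8.2 is discretionary and not tied to the label. Reported compliance follows SAP 12.6.1, and the exclusions in SAP 12.1.1 contain no capsule-compliance criterion. All of this stands and limits the reach of the error. It does not make the rule correct.
- **POP_L9 is only a mock shell.** True, but its footnote would print beside the compliance values and should match their derivation.
- **A protocol change needs ethics approval, and some counts or flags may not exist.** Protocol Appendix 3 does require the approval, and no document shows that flags were recorded. Both points bear on cost.

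**Conclusion.** The concern holds. Protocol 7.6 conflicts with protocol 7.1 and with SAP 12.6.1, and these passages, with the schedule of activities, must be reconciled. On matched intervals full adherence computes as 200% and half adherence as 100%, so the 80–120% band selects true adherence of 40–60%. On the literal intervals full adherence reaches 386% at Day 28 (without a Day 14 opening balance) and 680% at Day 90.

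The exact values rest on the assumptions listed with the calculation. The misclassification does not: no reading in capsules brings full adherence inside the band. The consequence is limited to the site-level label and the actions it may prompt.

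**What to change.** In protocol 7.6, replace the formula with:

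100 × (capsules on hand at the previous count + capsules dispensed since − capsules remaining or returned at this count − capsules lost) / (2 × days between the two counts)

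Apply the existing 80–120% limits to that figure. State that the Day 90 value runs from the Day 56 count, since none is scheduled at Day 80. Under the stated assumptions this gives 100% at every count. If clinic doses do come from separate stock, it gives 24/26 = 92%, 26/28 = 93%, 54/56 = 96% and 64/68 = 94%, all inside the band; saying which supply they come from would settle the point.

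In the POP_L9 footnote, replace *frequency* with 2 capsules per day, to match SAP 12.6.1. Recompute any noncompliance flags set under the printed formula. Where no Day 14 balance was kept, a Day 1 to Day 28 figure can be used instead: 54/(2 × 27) = 100% for full adherence.

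The cost is one formula in the protocol, with the approval an amendment needs; any site worksheet that copies it; one listing footnote; and a recalculation from recorded counts. No new data collection is needed.

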7.7. Concomitant Therapy

Medications and therapies not specifically prohibited by the study are allowed. Study participants must be on optimal maintenance therapy for COPD prior to screening, with no change in maintenance therapy for at least 4 weeks prior to baseline measurements and no anticipated changes between baseline and end of study. Any medication or vaccine (including over-the-counter or prescription medicines, vitamins, and/or herbal supplements) that the participant is receiving at the time of enrollment or receives during the study must be recorded along with:

1. reason for use
2. dates of administration including start and end dates

3. dosage information including dose and frequency

The Medical Monitor should be contacted if there are any questions regarding concomitant or prior therapy.

Use of the following medications with study treatment is prohibited during the study:

- Cholestyramine
- Oral steroids
- Any prescription drugs known to affect muscle mass, including androgen supplements, anti-androgens (such as LHRH agonists), anti-estrogens (tamoxifen, etc.), recombinant growth hormone, megestrol, etc.
- Strong inducers of CYP3A4 such as St John's Wort, Carbamezapine, Phenytoin and Rifampicin.

Of note, weaker CYP3A4 inducers are allowed.

A more complete listing of the different classes of CYP3A4 inducers can be found at Univ of Indiana School of Pharmacy website (<http://medicine.iupui.edu/clinpharm/ddis/main-table/>) or FDA website (<http://www.fda.gov/Drugs/DevelopmentApprovalProcess/DevelopmentResources/DrugInteractionsLabeling/ucm093664.htm#classInhibit>).

Although no evidence of lowering of blood glucose has been seen in phase I human studies of GSK2881078, improved glycaemic control has been observed with other SARMs, e.g. GTx-024, in healthy volunteers. Although the risk of a hypoglycaemic event in participants on diabetes treatments and GSK2881078 is considered very low, participants who are on medication (either oral medication or insulin) for diabetes should be counselled to monitor their blood glucose levels (where applicable) and remain alert for hypoglycaemic events. Participants should seek medical advice to adjust their diabetes treatment if they have any concerns in conjunction with advice from the Investigator and/or the Medical Monitor.

7.8. Treatment after the End of the Study

Participants will not receive any additional treatment from GSK after completion of the study because the indication being studied is not life threatening.

The investigator is responsible for ensuring that consideration has been given to the post-study care of the participant's medical condition, whether or not GSK is providing specific post-study treatment.

8. DISCONTINUATION CRITERIA

8.1. Discontinuation of Study Treatment

A participant may discontinue treatment if they have a severe exacerbation of COPD requiring hospitalization or if they meet liver or QTc stopping criteria. A participant who discontinues study treatment should return to the clinic only for the follow-up visit within the specified window if possible. Only the safety assessments for the follow-up visit (physical examination, 12-lead ECG, vitals, blood tests, urinalysis and concomitant medication review) should be conducted in these participants as described in the SoA and Section 9.4.

[figure not shown]

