8.1.1. Liver Chemistry Stopping Criteria

Liver chemistry stopping and increased monitoring criteria have been designed to assure subject safety and evaluate liver event etiology (in alignment with the FDA premarketing clinical liver safety guidance).

<http://www.fda.gov/downloads/Drugs/GuidanceComplianceRegulatoryInformation/Guidances/UCM174090.pdf>

Study treatment will be discontinued **for a participant** if liver chemistry stopping criteria are met:

Liver Chemistry Stopping and Increased Monitoring Algorithm

Liver Safety Required Actions and Follow up Assessments Section can be found in [Appendix 4](#) Liver Safety: Required Actions and Follow-up Assessments

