8.1.2. QTc Stopping Criteria

For trial eligibility and discontinuation, ideally the same QT correction formula will be used for *all* participants within a single trial. However, GSK does recognize that because multiple sites from different countries may participate in a single trial, this may not always be possible since QT correction formulae pre-programmed by different manufacturers within ECG machines tend to vary. In these situations, the same QT correction formula must be used throughout the trial for an individual participant.

- The QTc should be based on averaged QTc values of triplicate ECGs obtained over a brief (e.g., 5-10 minute) recording period.

A participant who meets either of the bulleted criteria below will be withdrawn from the study:

- QTc >500 msec OR Uncorrected QT >600 msec
- Increase from baseline of QTc >60 msec

For participants with underlying **bundle branch block**, follow the discontinuation criteria listed below:

Baseline QTc with Bundle Branch Block	Discontinuation QTc with Bundle Branch Block
<450 msec	>500 msec
450 – 480 msec	≥530 msec

See the SoA for data to be collected at the time of treatment discontinuation and follow-up and for any further evaluations that need to be completed.

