8.1.3. Temporary Discontinuation

Withdrawal of study treatment requires withdrawal from the study.

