8.2. Withdrawal from the Study

- A participant may withdraw from the study at any time at his/her own request, or may be withdrawn at any time at the discretion of the investigator for safety, behavioral, compliance or administrative reasons.
- If the participant withdraws consent for disclosure of future information, the sponsor may retain and continue to use any data collected before such a withdrawal of consent.
- If a participant decides to withdraw or is withdrawn by the responsible physician, the reasons for withdrawal and the results of any relevant tests will be recorded in the CRF and the planned follow-up procedures will be performed, where possible.
- If a participant withdraws from the study, he/she may request destruction of any samples taken and not tested, and the investigator must document this in the site study records.
- Refer to the SoA for data to be collected at the time of study discontinuation and follow-up and for any further evaluations that need to be completed. Only the safety assessments scheduled for the follow-up visit should be conducted in these participants as described in the SoA (Section 2).
- **Any participant who experiences a severe COPD exacerbation (i.e., associated with hospitalization or emergency room visit) or an exacerbation that requires treatment with oral steroids will be permanently discontinued from study treatment and should return to the clinic for the follow-up visit within the specified window if possible. Only the safety assessments scheduled for the follow-up visit should be conducted in these participants as described in the SoA (Section 2).**

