12.4. Appendix 4: Liver Safety: Required Actions and Follow-up Assessments

Liver chemistry stopping and increased monitoring criteria have been designed to assure subject safety and evaluate liver event aetiology (in alignment with the FDA premarketing clinical liver safety guidance).

<http://www.fda.gov/downloads/Drugs/GuidanceComplianceRegulatoryInformation/Guidances/UCM174090.pdf>.

Liver chemistry stopping criteria and required follow up assessments

Liver Chemistry Stopping Criteria – Liver Stopping Event	
ALT-absolute	ALT \geq 8xULN
ALT Increase	ALT \geq 5xULN persists for \geq 2 weeks
ALT Increase	ALT \geq 3xULN persists for \geq 4 weeks
Bilirubin^{1,2}	ALT \geq 3xULN and bilirubin \geq 2xULN (>35% direct bilirubin)
INR²	ALT \geq 3xULN and INR>1.5, if INR measured
Cannot Monitor	ALT \geq 3xULN and cannot be monitored weekly for 4 weeks
Symptomatic³	ALT \geq 3xULN associated with symptoms (new or worsening) believed to be related to liver injury or hypersensitivity

Required Actions and Follow up Assessments following ANY Liver Stopping Event

Actions	Follow Up Assessments

 • Immediately discontinue study treatment • Report the event to GSK within 24 hours • Complete the liver event CRF and complete an SAE data collection tool if the event also meets the criteria for an SAE² • Perform liver event follow up assessments • Monitor the subject until liver chemistries resolve, stabilize, or return to within baseline (see MONITORING below) • Do not restart/rechallenge subject with study treatment unless allowed per protocol and GSK Medical Governance approval is granted. • If restart/rechallenge not allowed per protocol 	
 • Viral hepatitis serology⁴ • Blood sample for pharmacokinetic (PK) analysis, obtained within 14 days after last dose⁵ • Serum creatine phosphokinase (CPK) and lactate dehydrogenase (LDH). • Fractionate bilirubin, if total bilirubin \geq 2xULN • Obtain complete blood count with differential to assess eosinophilia • Record the appearance or worsening of clinical symptoms of liver injury, or hypersensitivity, on the AE report form

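### Protocol 8.1 is looser than the protocol's own stopping rules, and its one-visit limit states no exception for the liver follow-up that Appendix 4 requires

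*Protocol*

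**What the plan says.** The general rule is in Protocol 8.1: "A participant may discontinue treatment if they have a severe exacerbation of COPD requiring hospitalization or if they meet liver or QTc stopping criteria". It adds that someone who stops "should return to the clinic only for the follow-up visit within the specified window if possible", with only that visit's safety assessments, and refers the reader to Section 9.4 for them.

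The specific rules read as follows.

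- **Liver (8.1.1 and Appendix 4).** Section 8.1.1: "Study treatment will be discontinued" when the criteria are met. Appendix 4, first listed action: "Immediately discontinue study treatment".
- **QTc (8.1.2).** "A participant who meets either of the bulleted criteria below will be withdrawn from the study".
- **Exacerbation (8.2).** A severe exacerbation, defined there by hospitalization or an emergency room visit, "or an exacerbation that requires treatment with oral steroids will be permanently discontinued from study treatment".
- **Assessments after stopping (8.2).** "Only the safety assessments scheduled for the follow-up visit should be conducted in these participants as described in the SoA".
- **Study status (8.1.3, headed Temporary Discontinuation).** "Withdrawal of study treatment requires withdrawal from the study".

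After any liver stopping event, Appendix 4 requires repeat chemistries within 24 hours (bilirubin or INR criteria) or 24 to 72 hours (all other criteria). Monitoring then continues twice weekly or weekly, respectively, until the values resolve, stabilize or return to baseline. It also asks for a PK sample within 14 days of last dose, viral hepatitis serology, CPK and LDH.

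**The concern.** Section 8.1 carries the title Discontinuation of Study Treatment, so it is where a site will look first. What it says differs from the detailed rules in two ways.

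First, it describes as possible what the other sections require, and it names fewer exacerbation triggers than 8.2.

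Second, it confines participants who have stopped to one visit about six weeks later. For a liver stopping event, Appendix 4 requires several contacts well before then. A site cannot follow both instructions literally.

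Raised ALT is the first risk listed in Protocol 3.3.1, and the mitigation given there relies on follow-up of participants who meet the liver stopping criteria. No endpoint, estimate or sample size depends on this point. What is at stake is whether the safety instructions for those participants read the same wherever a site looks.

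**Working it through.** The plan gives no figure to reproduce. The check compares text and then dates.

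**1. Stopping rule, trigger by trigger**

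| Trigger | Section 8.1 | Specific rule |
|---|---|---|
| Liver criteria | may stop | mandatory (8.1.1); immediate (Appendix 4) |
| QTc criteria | may stop | mandatory withdrawal (8.1.2) |
| Exacerbation with hospitalization | may stop | mandatory and permanent (8.2) |
| Exacerbation with emergency room visit | not named | mandatory and permanent (8.2) |
| Exacerbation treated with oral steroids | not named | mandatory and permanent (8.2) |

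Section 8.1 is weaker than the specific rule on three triggers and silent on two.

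**2. Can the one permitted visit deliver the Appendix 4 follow-up?**

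The limits to meet are a first recheck at 1 day or 1 to 3 days, and a PK sample by day 14 after last dose. The phrase *specified window* in 8.1 can be read in two ways.

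*Reading A: Protocol 5.1, 42 ± 7 days after last dose.*

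- Earliest: 42 − 7 = 35 days. Latest: 42 + 7 = 49 days.
- Against the PK limit: 35 − 14 = 21 days late, to 49 − 14 = 35 days late.

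*Reading B: Schedule of Activities window, study Days 126 to 140.* Days after last dose = visit day − last-dose day. As an assumption, the last dose is taken to fall on a scheduled post-baseline chemistry visit.

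| Last dose | Earliest | Latest |
|---|---|---|
| Day 14 | 126 − 14 = 112 | 140 − 14 = 126 |
| Day 28 | 126 − 28 = 98 | 140 − 28 = 112 |
| Day 56 | 126 − 56 = 70 | 140 − 56 = 84 |
| Day 90 | 126 − 90 = 36 | 140 − 90 = 50 |

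The earliest value under either reading is 35 days, which is beyond both limits. Weekly or twice-weekly monitoring cannot be met by a single visit on any date.

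**3. Content of the visit**

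Timing is not the only mismatch. The Schedule of Activities marks PK at the unscheduled visit but not at follow-up. It lists hepatitis B and C screening at screening only. CPK and LDH are not in the Appendix 6 chemistry panel. The routine follow-up assessments would therefore omit part of the Appendix 4 work-up whatever the date.

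**4. Is there an exception elsewhere?**

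- Section 8.1.1 points to Appendix 4 but does not say that Appendix 4 overrides the visit limit.
- Sections 8.1.2 and 8.2 refer to the Schedule of Activities for further evaluations. Its unscheduled-visit column marks clinical chemistry (including liver function tests) and PK. Footnote 1 to the schedule describes those assessments as optional, done as needed.
- Section 9.5.4 asks for clinically significant abnormal tests to be repeated until they settle. Section 9.3.3 requires serious adverse events to be followed until resolved or stabilized.

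These provide a route to the right follow-up. None of them qualifies the word *only* in 8.1 or 8.2.

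**The case against.** The strongest reply is that the opening of 8.1 is a lead-in. It lists grounds for stopping, and the subsections beneath it give the rule. *May* is weaker than *must* but does not forbid what *must* requires. This largely stands. A reader might infer that 8.1 permits continued dosing after a stopping criterion is met, or tells sites the opposite of the specific rules. The documents do not support that, because every specific rule is mandatory and the exacerbation rule in 8.2 is printed in bold.

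The second reply is that *only* was meant to drop routine functional tests, not event-driven safety care. The Amendment 2 entry on Schedule of Activities footnote 2 fits this: it confines withdrawn participants to safety assessments and deletes a line giving the leg press priority. Section 8.1 is also softly worded (*should*, *if possible*). Besides the text in step 4 of the working, Section 5.1 provides unscheduled visits for unresolved findings, 9.3 keeps adverse events that led to discontinuation under follow-up, and Appendix 4 makes the bilirubin and INR events serious, so 9.3.3 applies to them. This stands as a reason to expect correct handling. It does not supply the missing exception, and liver events that stop treatment on ALT alone are not automatically serious.

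Third, a reader might infer a further conflict between 8.1.3, which ties stopping drug to leaving the study, and Appendix 4, which lets the participant remain for follow-up. That is thin. Section 8.1.3 is headed Temporary Discontinuation and most naturally rules out pausing and restarting. Section 8.2 in any case keeps follow-up procedures going after withdrawal, where possible.

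**Conclusion.** The point holds as a wording contradiction in safety instructions, of modest severity. Section 8.1 is permissive where the specific rules are mandatory, and it names a narrower exacerbation trigger. Its visit limit, with the matching assessment limit in 8.2, has no stated exception for Appendix 4. Followed literally, it would omit required liver follow-up.

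The 35 to 49 days, and the 21 to 35 days past the PK limit, show only that the two instructions are incompatible. A reader might take them as a predicted delay in liver checks. They are not, because unscheduled visits are available and a careful site would probably follow Appendix 4. The documents give no basis for a number of participants affected or checks missed.

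The incompatibility does not depend on which visit window is meant. The Reading B ranges rest on assumed last-dose days, but the conclusion does not need them. One reservation: the liver algorithm in 8.1.1 is a figure whose content was not available to me. It could add to the guidance for sites, but it would leave the sentences in 8.1 and 8.2 as they are.

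**What to change.** Amend the wording as follows.

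- **8.1, stopping rule.** Replace *may discontinue treatment* with *will be permanently discontinued from study treatment*, and use the full 8.2 exacerbation triggers: hospitalization, emergency room visit, or oral steroid treatment.
- **8.1 and 8.2, after the visit and assessment limits.** Add: *except that liver event follow-up under Appendix 4 and repeat of clinically significant abnormal tests under Section 9.5.4 must be completed, using unscheduled visits as needed*.
- **8.1, cross-reference.** Change Section 9.4 (treatment of overdose) to Section 9.5 (safety assessments), which 9.1.5 already cites.
- **8.1.3, optional.** State that participants who are withdrawn still complete this safety follow-up.

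The cost is wording in the next amendment. It adds no visit, test or participant beyond what Appendix 4, 8.2, 9.5.4 and the unscheduled-visit column already require or provide for.
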